Cover Page

The effect of blood flow restriction training on rotator cuff strength in the healthy, untrained shoulder

Date: July 19, 2019

Pro00017362

NCT: 04530367

Status: Closed 12/7/2021

1) Protocol Title

The effect of blood flow restriction training on rotator cuff strength in the healthy, untrained shoulder

2) Investigator

[name]

3) Objectives

The aim of this study will be to determine the effect of upper extremity (UE) blood flow restriction (BFR) training for muscular strength improvement in individuals with no history of previous shoulder injury. The authors hypothesize that, participants who partake in BFR training will experience greater strength gains compared to a control group performing the same exercises.

4) Background

BFR training has been gaining popularity as a novel technique to develop greater strength and muscle mass in the rehabilitation setting. Many high-quality studies have examined the effects of muscle growth following controlled programs targeting strengthening at lower loads than typically used for hypertrophy. In rehabilitation, this provides the patient a significant advantage when muscular weakness and poor neuromuscular control predominate following an injury or surgery. If an individual is able to attain measurable improvements in muscle function utilizing low loads, then rehabilitation can be safer and more productive.

Recent publications have described the effects of BFR with exercise, including increases in muscle fiber hypertrophy at the cellular level^{12,17,19,20}, muscle size and strength improvements with various methods of exercise^{2,6,10,26}, and decreased muscle atrophy following injury or surgery.^{14,21} In resistance training, muscle hypertrophy is carried out by mechanical tension and metabolic stress. It's hypothesized that metabolic stress factors play the dominant role in BFR training.¹ In horses, somatotropin, a hormone that induces the release of growth hormone, is significantly increased after a BFR walk for 5 minutes as compared with a control.¹⁴ The somatotropin remained elevated at the 15 minute and 60 minute intervals. In humans, multiple studies have shown a significant increase in growth hormone following BFR with low resistance exercise as compared with high resistance exercise.^{20,23} In addition to increased growth hormone expression, myogenic and proteolytic mRNA expression has been studied in human subjects undergoing low resistance BFR exercise. Interestingly, myogenic mRNA expression is unchanged. However, proteolytic gene (FOXO3A, Atrogin-1, and MuRF-1) expression is downregulated as compared to patients without BFR.^{12,17} Gene expression of myostatin, a protein that inhibits myogenesis, was shown to be downregulated in a patient with inclusion body myositis after undergoing BFR low resistance exercises.¹⁷

Interestingly, one may speculate that muscles proximal to the occlusion cuff may not experience similar strength gains as found in those distal to the cuff. However, a systematic review by Dankel et al. (2016) found several instances of proximal gains in muscle size and strength.⁸ Suggested mechanisms for this phenomenon include the typical high repetition characteristic of BFR exercises (upwards of 75 total repetitions per exercise)⁸, purported synergistic effects of proximal musculature as the distal muscles fatigue³ and higher recruitment of type II muscle

activation²⁵, and muscle cell swelling occurring during BFR.¹¹ This is important for future research of the utilization of BFR with proximal musculature.

What is currently unknown are the potential for improvements in strength of musculature proximal to the occluding cuff during BFR training. The rotator cuff serves as an excellent example due to its proximal location to typical UE placement as well as documented EMG specificity with certain exercises.^{4,5,15,16} Any strength gains, if elucidated with given program, should be easily detectable. Data from this study may possibly provide foundational information for future studies utilizing similar methods with different populations

The most frequently encountered side effects of BFR training is bruising and muscle soreness at the tourniquet site.^{12,25} BFR exercise does not show increase in markers for muscle damage such as myoglobin or creatine kinase.³ Deep vein thrombosis is infrequently seen at a rate of less than .1%.^{12,24}

5) Setting of the Human Research

The research will be conducted in an outpatient physical therapy clinic under close supervision of a trained and licensed physical therapist. Additional locations may include: Rice University Campus [name].

6) Resources available to conduct the Human Research

Equipment required for study will include: Delfi PTS Blood Flow Restriction Tourniquet System, MicroFET 2 hand-held dynamometer, cable column machine, free weights, VICON motion capture system.

7) Study Design

Study participants will be randomly allocated in to 3 groups: control group (no exercise), exercise group, and BFR + exercise. Power analysis indicates the need for approximately 20 individuals in each group. Each exercise group will perform the same set of exercises 2 days/week for 8 weeks on their non-dominant upper extremity. Each group will also undergo strength testing at the same time throughout the protocol. Whereas the control group will only undergo testing in the same time periods. Muscle strength testing will be performed before the initiation of the program, at 4 weeks, and upon conclusion of the program. Testers will be blinded to group allocation. Muscle testing will be performed using manual hand-held dynamometry consistent with literature describing appropriate methods.^{9,18} Each manual muscle test will be performed as maximal exertion one repetition maximum test (1RM) three times to ensure most accurate dynamometry reading. For any baseball pitcher participants, motion capture measures will be taken before week 1 and after week 8. This will include sensors that measure range of motion and arm biomechanics for a maximum of 25 pitches in each session. To ensure test-retest reliability, each participant will undergo testing by the same individual. A familiarization protocol will be enforced to ensure all participants are familiar with testing measures and to decrease the amount of variability in intratester performance.

Exercises are as follows:

1. Cable column external rotation (at 90 degrees of abduction)
2. Cable column internal rotation (at 90 degrees of abduction)

3. Sidelying external rotation with weight (0 degrees)
4. Standing scaption with weight
 - These exercises have been found to incorporate the greatest electromyographic muscle activity of the rotator cuff in the literature.^{4,5,15,16}
 - The order of exercises will remain same for each participant in each group

BFR tourniquet placement will occur at the most proximal portion of the upper extremity. Tourniquet pressure will be applied at 50% of maximal limb occlusion pressure, to be re-measured each week. This is consistent with current literature recommendations for upper extremity BFR training.^{6,8,13}

Resistances for each exercise will be determined by using 10-30% of 1RM (found during testing). This is consistent with current literature recommendations for upper extremity BFR training.^{6,8,13} Resistance may be increased as the subject tolerates so long as they stay within the 10-30% 1RM range. Following strength testing at 4 weeks, resistances may be adjusted due to strength gains.

a) Recruitment Methods

Potential study participants will be recruited from the local area who will be able to access clinic and equipment. Participants will be surveyed to ensure all inclusion and exclusion criteria are met.

b) Inclusion and Exclusion Criteria

Inclusion: participants must be healthy, untrained, volunteers who accept all provisions of the study and agree to complete the program in its entirety. Ages accepted will be 18-65.

Exclusion: potential participants will be excluded if:

1. Previous history of shoulder injury occurring in the laterality of choice
2. Current painful dysfunction resulting in exercise limitation
3. Any health-related exercise limitation as ordered by physician
4. Vascular compromise or previous vascular surgery
5. Ages outside of 18-65
6. Inability to access clinic and equipment
7. Currently involved in structured strength training regimen of the upper extremity

c) Study Endpoints

Exercise programs for each individual will terminate upon the completion of 16 sessions over 8 weeks. If any subject reports adverse effects (pain, injury, decreased range of motion), their program will be terminated and referral given for treatment by physician. Subject recruitment will occur over the course of 6-12 months or until reasonable power is achieved.

d) Procedures involved in the Human Research

Eligibility will be explained during the consent process with each participant. Minimal risk will be explained to the patient regarding exercise and blood-flow restriction training.

e) Data management

The PI will be responsible for all data collected, its confidential storage, and deletion after the study is completed.

f) Withdrawal of subjects

Subjects may withdraw at any time for any reason. Their data will be included if the individual has performed at least 4 weeks of the program. If the individual withdraws prior to 4 weeks, any pre-program testing will be deleted.

8) Risks to subjects

Minimal risks are present but may include arm pain due to tourniquet pressure or possible deep vein thrombosis.

9) Potential benefits to subjects

Subjects in either group may experience strength gains consistent with a strength-training program.

10) Provisions to protect the privacy interests of subjects

PHI information will not be used or published in the study as all information will be used to form aggregate data. The data will be kept on a secure password protected, hospital server and will be deleted after the study is complete. Subject data will be coded according to initial randomized group allocation.

11) Provisions to maintain the confidentiality of data

See #10

12) Cost to subjects

No costs will be incurred to the subjects.

13) Consent process

Participants will be educated on the data accrual process when they obtain the inclusion survey. Participation is completely voluntary and submission of declaration of inclusion is mandatory to be allocated to grouping and undergo testing/exercise program.

14) Process to document consent in writing

The standard consent form for this project will be explained and if the subject wishes to participate the consent will be signed prior to the start of the questionnaire.

RESOURCES:

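### Does training only the non-dominant arm undermine the motion capture taken in baseball pitchers?

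*Combined protocol and SAP*

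**What the plan says.** Section 7) Study Design sets the trained side for both exercise groups: "Each exercise group will perform the same set of exercises 2 days/week for 8 weeks on their non-dominant upper extremity". It makes no exception for pitchers.

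The same paragraph then adds a measure for a subset of participants: "For any baseball pitcher participants, motion capture measures will be taken before week 1 and after week 8". Its content is given as follows: "This will include sensors that measure range of motion and arm biomechanics for a maximum of 25 pitches in each session". Neither the throwing arm nor the sensor arm is named, and no purpose is stated for the measure.

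The other elements that depend on an arm are worded more loosely. On strength testing, section 7 says "Each group will also undergo strength testing at the same time throughout the protocol", without a side. On the tourniquet it says "BFR tourniquet placement will occur at the most proximal portion of the upper extremity", again without a side. The first exclusion criterion in section 7 b) is "Previous history of shoulder injury occurring in the laterality of choice", whereas section 3) Objectives describes the aim as being "for muscular strength improvement in individuals with no history of previous shoulder injury".

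The gap the study addresses is stated in section 4) Background: "What is currently unknown are the potential for improvements in strength of musculature proximal to the occluding cuff during BFR training".

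**The concern.** The capture sessions bracket the training programme, so they read as a before-and-after measure of its effect. Yet the programme is given to the non-dominant arm, and pitching is an act of the throwing arm. If the throwing arm is the dominant one, the shoulder doing the pitching was neither exercised nor placed under restriction. A change in its mechanics could then not be read as a direct training or blood flow restriction (BFR) effect on that shoulder. The Background does not present cross-limb transfer as an aim: the gap it names concerns muscle proximal to the cuff.

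The loose naming of the arm adds to the unease. If the tested arm differed between groups, the strength comparison itself would suffer. If the first exclusion covers only the studied arm, a pitcher with a past injury to the throwing shoulder could enter, although the aim speaks of people with no such history.

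**Working it through.** The concern contains no planned figure to reproduce. The only design number, about 20 participants in each of three groups, does not depend on which arm is recorded. The check is therefore mainly a comparison of the text.

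**1. Does the capture miss the trained shoulder?** Two facts are needed, and the documents give neither.

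- Let *p* be the share of exercise-group pitchers who throw with the arm classed as non-dominant.
- Let *q* be the share of sessions with sensors on the throwing arm only; in the rest, both arms carry sensors.
- Share of sessions missing the trained shoulder = (1 − *p*) × *q*.

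Both values are assumptions:

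| *p* | *q* = 1 (throwing arm only) | *q* = 0 (both arms) |
|---|---|---|
| 0 | (1 − 0) × 1 = 100% | 0% |
| 0.05 | (1 − 0.05) × 1 = 95% | 0% |
| 0.10 | (1 − 0.10) × 1 = 90% | 0% |

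The answer turns almost wholly on sensor placement, which is not stated. The supportable reading is that the text does not establish that the trained shoulder is recorded, which is weaker than saying it is not recorded. The share of these pitchers whose *throwing* arm is untrained is 1 − *p* in either column. That part of the concern needs only the first assumption.

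**2. What could the capture data still show?** Participants are randomised to three groups, one of which does no exercise. A between-group difference in an untrained throwing arm could still reflect allocation, though by an indirect route. Section 4 also reports growth hormone rises with BFR, a mechanism not clearly confined to the cuffed limb, although the protocol never links it to the other arm. The mismatch limits interpretation to an indirect effect. It does not by itself bar inference.

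**3. Is the strength comparison exposed?** Section 7 sets exercise loads as a percentage of the one-repetition maximum found at testing. Testing in the two exercise groups must therefore include the trained arm. The hypothesis in section 3 compares BFR participants with a group doing the same exercises, which is the contrast between those two groups, so the tested arm is settled for it. Only the no-exercise group's tested arm is left open, and the obvious choice is the arm tested in the others. The tourniquet sentence needs no side either, since the cuff goes on the limb being exercised.

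**4. Is the eligibility wording a contradiction?** The side referred to in the first exclusion reads naturally as the study side, which section 7 fixes as non-dominant. Two other exclusions, for current painful dysfunction and for physician-ordered exercise limits, are not tied to a side. What remains unscreened is a past, resolved injury to the other shoulder. For the strength objective, that shoulder is not the one being trained.

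**5. How many participants are affected?** The number of pitchers is not given and may be zero. Entry requires untrained volunteers and excludes anyone in structured upper-extremity strength training.

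**The case for a change.** The best case for a change is that the two statements stand in one paragraph, the fix would cost a few sentences, and nothing in the protocol explains why an untrained throwing arm should be studied. Even with sensors on both arms, the arm doing the pitching is untrained if pitchers throw with the dominant arm. The controls' tested arm is also unnamed, and that touches a strength comparison rather than a side measure.

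Much of this stands. The measure is poorly motivated as written, the side is not named in common terms, and any effect seen in an untrained throwing arm would have to be described as indirect. What does not stand is the step from there to a needed change. Dropping the capture, or ruling out any exercise or BFR inference from it, goes further than the mismatch justifies under randomisation. It would also be a debatable choice about a measure for which no analysis is planned. A count of how many arm-dependent elements name a side is no measure of harm, because context settles most of them.

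**Conclusion.** No change to the plan follows. The tension between training the non-dominant arm and recording pitching is real, but its size cannot be fixed from the documents: between 0% and 100% of exercise-group pitchers' sessions could miss the trained shoulder, depending on unstated throwing arm and sensor placement. It affects a subgroup that may be empty and a measure without a stated hypothesis, endpoint or analysis. The strength objective, sample size and randomisation are untouched.

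The loose naming of the tested and screened arm is missing detail that analysts would fill sensibly. This conclusion assumes that the same arm is strength-tested in controls as in the exercise groups, and that the first exclusion refers to the study arm. Both are the natural readings. The choice of arm remains the investigators'. Any report of the pitching data would need to say which arm was recorded and treat an effect in an untrained arm as indirect.

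### Does ending recruitment at an undefined reasonable power leave the sample size open to the accumulating results?

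*Combined protocol and SAP*

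**What the plan says.** Two places bear on the sample size, both in section 7 of the combined document.

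- The opening of section 7 (Study Design) sets the size: "Power analysis indicates the need for approximately 20 individuals in each group". There are three groups: "Study participants will be randomly allocated in to 3 groups: control group (no exercise), exercise group, and BFR + exercise". This makes about 60 people if allocation is equal, which the per-group figure implies but the text does not state.
- Section 7 c) (Study Endpoints) says when recruitment ends: "Subject recruitment will occur over the course of 6-12 months or until reasonable power is achieved".

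On who sees what, section 7 says "Testers will be blinded to group allocation" and does not mention blinding of anyone else. Strength is tested at baseline, 4 weeks and 8 weeks. On loads, the document says "Following strength testing at 4 weeks, resistances may be adjusted due to strength gains". For people who leave early, section 7 f) says "Their data will be included if the individual has performed at least 4 weeks of the program".

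No section describes an interim analysis, a sample-size re-estimation or a calculation of observed power. Nor does any section give the alpha, target power, effect size or SD behind the 20 per group.

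**The concern.** A stopping rule phrased in terms of power, with no threshold and no cap, can be read in three ways:

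1. Stop at the planned head-count.
2. Stop when a pooled, blinded variance estimate suggests enough people.
3. Stop when the group difference seen so far looks adequately powered.

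The third reading makes the final number depend on the treatment effect being tested, and an unadjusted 5% test then no longer has exactly a 5% error rate.

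The opportunity exists. Follow-up lasts 8 weeks and recruitment 6 to 12 months, so many final results would be available before recruitment closed, and only the testers are said to be blinded. Individual strength results are also used during the study to set loads. At stake would be the error rate of the main comparison (Objectives: "participants who partake in BFR training will experience greater strength gains compared to a control group performing the same exercises"), and a reader's ability to tell whether the final number came from the plan, the calendar or the data.

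**Working it through.** **1. The plan's own figure.** The 20 per group cannot be reproduced, because its inputs are not given. It can be solved backwards. Assuming 80% power, a two-sided 5% test and two groups of n = 20, the standardised difference is

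d = (1.960 + 0.842) × √(2/20) = 2.802 × 0.316 = 0.89 (0.91 with the t distribution).

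So 20 per group is what an ordinary calculation gives for a large effect. It is a definite number for the phrase in 7 c) to point to.

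**2. How many results exist before recruitment closes.** Assume 60 people enrol evenly with no dropout.

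- Over 26 weeks: 60 × (26 − 8)/26 = 41.5 people have week-8 results.
- Over 52 weeks: 60 × (52 − 8)/52 = 50.8.
- People per group still in progress at any moment: 60 × 8/26/3 = 6.2 and 60 × 8/52/3 = 3.1.

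The opportunity to look is therefore real, but no look is planned.

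**3. Error rate under each reading.** The comparison is BFR plus exercise against exercise alone, with no true effect and a two-sided 5% t-test. The looks at 10, 15 and 20 per group are assumed. Simulations used 1,000,000 trials (200,000 for the pooled-SD case).

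| Reading | False-positive rate |
|---|---|
| Stop at the head-count of 20 per group | 5.0% |
| Stop on a blinded pooled SD (planning difference 0.8 to 1.1 SD, assumed) | 5.0–5.1% |
| Stop on observed power of at least 80%, the 3 to 6 per group in progress also analysed | 5.1–5.3% |
| The same, those in progress left out | 5.5% |

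A repeat simulation of the head-count and observed-power rows agreed to within 0.1 percentage point.

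**4. Why even the third reading does so little.** Observed power reaches 80% only when |t| exceeds its critical value by about 0.84. At 10 per group that means |t| ≥ 2.10 + 0.84 = 2.94, a p-value of about 0.009. At 15 per group it means |t| ≥ 2.05 + 0.84 = 2.89, a p-value of about 0.007. Early stops are therefore rare when there is no effect. Analysing those still in progress dilutes them further, and section 7 f) supports analysing them, since it keeps even people who withdraw after 4 weeks.

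**5. What a calendar stop would cost.** The half-width of the 95% interval for a difference, in SD units, is t × √(2/n).

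- 20 per group: 2.024 × √(2/20) = 0.64
- 15 per group: 2.048 × √(2/15) = 0.75
- 10 per group: 2.101 × √(2/10) = 0.94

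This is a loss of precision, not a bias. It follows from slow recruitment however the sentence is worded.

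**6. The load-setting results.** Adjusting one person's load from that person's own week-4 test compares no groups and uses no week-8 result, and the control group has no loads to set. It is not evidence of a look at the comparison.

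**The case for a change.** The best case for a change is that the sentence is the only recruitment rule in the document and does not fix a number. With no effect size stated, the size needed for 80% power (two-sided 5%, normal approximation) runs from 11 per group at d = 1.2 to 99 at d = 0.4, so two careful people could stop at very different points and both claim to comply. The calendar bound is itself a range. The investigator is responsible for all the data, which are coded by randomised group (section 10), and nothing keeps the results away from the decision to stop. The Background also says "Data from this study may possibly provide foundational information for future studies utilizing similar methods with different populations", so later readers may want to know how the size arose. Writing the intent down would take two sentences.

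Some of this stands. The phrase is undefined, it does not refer back to the 20 per group, and the document does not say that group results play no part. But the range of 11 to 99 arises only if the sponsor's own power statement is set aside. That statement is the only one in a short protocol, and it sits in the same section. The proposed wording would mostly restate the sponsor's own 20 per group and 12 months, and it would not prevent a shortfall. Traceability is the remaining cost. A final number near 60 would be consistent with the plan, so the question becomes live only if the reported number departs clearly from that.

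**Conclusion.** No change is needed. This is a loosely worded sentence with a missing cross-reference, which a reader of section 7 fills sensibly: recruit about 20 per group within the 6 to 12 month window. On that reading the error rate is 5.0%. On the least favourable reading the wording reasonably supports at the planned size, stopping on observed power, it is about 5.1% to 5.3%, or 5.5% if people in progress were left out of the analysis, which nothing in the document suggests.

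These figures rest on assumptions: a two-sided 5% t-test, looks at 10, 15 and 20 per group, even accrual and no dropout. Larger inflation would need stopping on a significant p-value or recruiting well past the planned size. The document mentions neither. A shortfall at the calendar limit would widen the interval from 0.64 SD to as much as 0.94 SD if only 10 per group were reached, and the group sizes in the report would show it. The cover page also marks the study as closed, so rewording the recruitment rule now would not alter how the sample was obtained.

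### Section 7 f) drops randomised participants who withdraw before week 4 and deletes their pre-program strength test: the first can bias BFR against exercise, the second rules out any baseline-based analysis of early leavers

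*Combined protocol and SAP*

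**What the plan says.** Section 7 f) lets participants withdraw at any time and then sets a two-part data rule. On inclusion: "Their data will be included if the individual has performed at least 4 weeks of the program". On earlier leavers: "If the individual withdraws prior to 4 weeks, any pre-program testing will be deleted".

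Section 7 sets the test times: "Muscle strength testing will be performed before the initiation of the program, at 4 weeks, and upon conclusion of the program". An early leaver's pre-program test is therefore the only scheduled strength value that person has. Section 7 also provides for random allocation to three groups (no-exercise control, exercise, BFR plus exercise) of about 20 each. Of the no-exercise group it says: "Whereas the control group will only undergo testing in the same time periods".

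The hypothesis in section 3 is that "participants who partake in BFR training will experience greater strength gains compared to a control group performing the same exercises", so the main contrast is BFR v exercise. Section 7 c) adds: "If any subject reports adverse effects (pain, injury, decreased range of motion), their program will be terminated". Section 8 says: "Minimal risks are present but may include arm pain due to tourniquet pressure". Section 4 names bruising and muscle soreness at the tourniquet site as the most frequent side effects.

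The document defines no analysis population, missing-data method or sensitivity analysis, and no strength test after a participant stops.

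**The concern.** The rule selects participants by something that happens after randomisation. Those left in each arm are comparable only if leaving early is unrelated to strength gain, or if the loss and its relation to gain are the same in both arms. Unequal loss is plausible from the protocol itself, because only the BFR arm wears the tourniquet and the named side effects come from it.

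The two parts of the rule do different harm:

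- **Exclusion, with no later test.** This can shift the estimated BFR effect and raise the false-positive rate.
- **Deletion of the baseline.** This is irreversible. It prevents a baseline table of everyone randomised, a comparison of leavers with stayers, and any imputation that uses baseline strength. The sentence does not cover counts of leavers by arm, which may survive.

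Two wording gaps add to the problem. The rule does not say what 4 weeks of the program means for control participants, who have no program. Nor do sections 7 c) and 7 f) say whether a program ended for adverse effects counts as a withdrawal.

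**Working it through.** **Inputs from the protocol.** About 20 per group (section 7); tests before the program, at 4 weeks and at the end (section 7); the inclusion and deletion rules (section 7 f). The power analysis behind 20 per group cannot be reproduced, because its effect size, SD, alpha and power are not given.

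**Assumptions.** Early-loss rates p_BFR and p_EX; leavers' mean gain lower than stayers' by δ SD, the same δ in both arms; no true effect among all randomised; two-sided 5% t-test.

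**Step 1: bias from the exclusion.** With an overall mean gain of 0 in each arm, the stayers' mean is p × δ. The retained-only contrast is therefore

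bias = δ × (p_BFR − p_EX).

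For 20% v 5% and δ = 1, this is 1 × (0.20 − 0.05) = 0.15 SD. The simulated results below use 200,000 trials per case with 20 randomised per arm.

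| Early loss, BFR v exercise | δ (SD) | Bias (SD) | Two-sided error |
|---|---|---|---|
| 10% v 5% | 1 | 0.05 | 5.3% |
| 20% v 5% | 0.5 | 0.075 | 5.5% |
| 20% v 5% | 1 | 0.15 | 7.1% |
| 30% v 5% | 1 | 0.25 | 10.5% |
| 20% v 20% | 1 | 0 | 5.0% |
| 5% v 20% | 1 | −0.15 | 7.1% |
| 20% v 5% | 0 | 0 | about 5% |
| 20% v 5% | −1 (leavers gain more) | −0.15 | 7.2% |

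Hand check of the third row by normal approximation: 16 and 19 are retained, so SE = √(1/16 + 1/19) = 0.339 and 0.15/0.339 = 0.442. The error is 1 − Φ(1.96 − 0.442) + Φ(−1.96 − 0.442) = 0.0645 + 0.0082 = 7.3%, in line with the simulated 7.1%.

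**Step 2: what later testing would recover.** If every leaver is tested and kept, the bias is 0 and the error about 5%. If only a share r return, the missing share is m = p(1 − r), and each arm's analysed mean is shifted by m(1 − p)δ/(1 − m). For 20% v 5% and δ = 1:

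- r = 0.5: 0.10 × 0.80/0.90 − 0.025 × 0.95/0.975 = 0.089 − 0.024 = 0.065 SD.
- r = 0.25: 0.15 × 0.80/0.85 − 0.0375 × 0.95/0.9625 = 0.141 − 0.037 = 0.104 SD.

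**Step 3: what the deletion adds.** In a baseline-adjusted model at 20% v 5% and δ = 1, the bias is 0.150 SD with baselines deleted and 0.150 SD with them kept and used for regression imputation. The two must agree, because imputing fitted values leaves the regression coefficients unchanged. With 5 leavers and 35 stayers (20% of 20 plus 5% of 20, out of 40), the lost baseline comparison would have SE = √(1/5 + 1/35) = 0.48 SD, so it could only be descriptive.

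**Step 4: how likely the rule is to be used.** P(at least one early leaver) = 1 − (1 − p)^n. Among the 40 in BFR and exercise this is 1 − 0.98^40 = 55% at 2% loss and 1 − 0.95^40 = 87% at 5%. Among all 60 it is 70% and 95%.

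**Step 5: power.** The difference detectable with 80% power rises from 0.91 SD (20 v 20) to 0.95 SD (18 v 19) or 0.98 SD (16 v 19). Power loss is not the main issue.

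**The case against.** The strongest reply is that section 7 f) is not the real source of the bias. Someone who leaves before week 4 has no later strength value, so striking out the rule would not supply a gain to analyse; Step 3 confirms that keeping the baseline alone changes nothing. This stands. The bias comes from the exclusion together with the absence of testing after stopping, and both need attention.

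The size is also wholly assumed. Participants are healthy "volunteers who accept all provisions of the study and agree to complete the program in its entirety", the risks are described as minimal, and the stop in section 7 c) applies to any subject, so early loss may be low or similar across arms. An error above 10% needs 30% v 5% loss and a 1 SD gap, which nothing in the documents supports. This stands as a limit on weight, but it does not justify the rule.

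The remedy is partial. Those who withdraw may not return, and those stopped for pain or injury may not be suitable for a maximal-exertion test. Step 2 shows the bias left behind, which is why a sensitivity analysis is needed as well.

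Finally, the hypothesis refers to those who take part, so making all randomised primary is partly a choice of estimand. That is fair. But the 4-week set does not safely answer that question either, unless leaving is unrelated to gain.

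**Conclusion.** The concern holds and should be fixed. Section 7 f) states an exclusion after randomisation, and nothing elsewhere in the document offsets it. For the effect of assignment, under the assumptions used, the bias runs from 0 to about 0.25 SD in either direction, with a two-sided error between 5% and about 11%. Modest unequal loss (10% v 5%) gives only 0.05 SD. Whether any bias occurs depends on loss being both unequal and related to gain; the documents make the first plausible and are silent on the second.

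The deletion is a separate and lesser harm. It adds no bias in the cases examined, but it is permanent and costs transparency and options for analysis. Privacy does not explain it, because section 10 already keeps study data on a secure server until the study is complete. Whether the consent terms require deletion cannot be checked here, since the consent pages are not available.

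**What to change.** Replace the data rule in section 7 f) as follows.

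1. Keep data already collected, with the reason for leaving, unless the participant withdraws consent to their use and the consent terms require deletion. Kept data stay under the section 10 safeguards until study end.
2. Invite participants who stop the program but have not withdrawn consent to the already scheduled week-4 and week-8 tests, where the study's clinicians judge this suitable.
3. State the estimand. As primary, analyse all randomised participants in their allocated group with a repeated-measures model on baseline, week 4 and week 8.
4. For those with no later test, add a sensitivity analysis that shifts their assumed gain from −1 to +1 SD.
5. Make the 4-week set a secondary or sensitivity analysis, and define what it means for controls.
6. Report losses and adverse effects by arm.
7. Reconcile sections 7 c) and 7 f) on whether a program ended for adverse effects counts as withdrawal. No clinical rule is proposed.

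The cost is protocol wording, a check of the consent terms and a few extra test visits. The estimated effect may be smaller because non-completers count. No new data storage is needed.

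The cover page lists the study as closed, so deleted baselines may be unrecoverable. If so, the report can still give counts and reasons by arm where records survive, label the analysed set for what it is, and run the shift analysis on unadjusted gain, which needs only the counts of leavers by arm.
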